#### 4.6. Interim Analyses

No interim analysis is planned for this study.

## 4.7. Final Analyses

The final analysis will be conducted after the database is locked.

 If not obtained as standard of care  $\leq$ 6 weeks (Cohort A) or  $\leq$  4 weeks (Cohort B) prior to Day 1. If Na- $^{18}$ F-PET bone scans conducted at screening must be at least 10 hours prior to dosing.

# 5. GENERAL CONSIDERATIONS FOR DATA ANALYSES AND HANDLING

# 5.1. General Summary Table and Individual Subject Data Listing Considerations

Adverse event and medical history verbatim terms will be coded using the Medical Dictionary for Regulatory Activities (MedDRA), version 4.0. Medications will be coded using the World Health Organization Drug Dictionary (WHODDE) from December 2016.

Summary tables and listings will include the following information: dataset(s) used in table production, date of data extract, date of output generation, the SAS program name and location (directory path), page x of y numbering. Adverse event and medical history summaries will indicate the MedDRA version; prior and concomitant medication summaries will indicate the WHODD version.

Summary tables for demographics and baseline characteristics, medical history, exposure, concomitant medications, and safety will include the following columns: Cohort A, Cohort B, overall (Cohorts A and B combined). Efficacy tables will be produced by cohort.

# 5.2. General Post Text Summary Table and Individual Subject Data Listing Format Considerations

Statistical analyses will be performed, and datasets and tables will be generated using SAS version 9.4 (SAS Institute, Inc., Cary, NC, USA).

#### 5.3. Data Presentation Conventions

Continuous data will be summarized using descriptive statistics [i.e., N, arithmetic mean, standard deviation (SD), median, minimum, and maximum]. The minimum and maximum will be displayed to the same level of precision as collected data; mean and median will be displayed to one level of precision greater than the data collected; SD will be displayed to two levels of precision greater than the data collected. Categorical data will be described using frequencies and percentages. A row for missing values will be included, when applicable. P-values will be presented at four decimal places.

Dates will be presented in DDMMMYY format and times will be presented as HH:MM using a 24-hour clock.

In tables and listings, columns of data will be decimal aligned.

## 5.4. Analysis Populations

#### **5.4.1.** Consented Set

All subjects who sign an informed consent document will be included in the consented set.

#### 5.4.2. Safety Set

All subjects who receive any amount of F-DCFPyL will be included in the safety set.

#### **5.4.3.** Evaluable Set

*Evaluable subjects* in Cohort A are those who were dosed, had a prostatectomy or lymphadenectomy, and provided a F-DCFPyL PET image result (positive or negative) and a corresponding histopathology result (positive or negative).

Evaluable subjects in Cohort B are those who were dosed, received a conventional image guided biopsy, and provided a F-DCFPyL PET image result (positive or negative) and a corresponding histopathology result (positive for prostate cancer or negative), along with a conventional image that confirms the location of the histopathology sample.

#### 5.4.4. Change in Planned Protocol Procedure Set

The change in planned protocol procedure set includes dosed subjects in Cohort A who did not have a prostatectomy and lymphadenectomy due to change of planned management, and subjects in Cohort B who did not have conventional guided biopsy due to change of planned management. See figure 1 above for definition of change in planned management.

#### 5.4.5. Per Protocol Set

The Per-protocol set is defined as subjects in the Evaluable set without any major protocol deviations. Major protocol deviations will be identified prior to database lock and analysis.

#### 5.4.6. PK Blood Set

Subjects who provide at least six of the nine scheduled blood samples.

#### 5.4.7. PK Urine Set

Subjects who provided at least two of the three scheduled urine samples.

#### 5.5. Derived and Transformed Data

#### **5.5.1.** Baseline Definition

Baseline will be the latest pre-dose value.

#### 5.5.2. Baseline Age

Age is computed in the database as the number of full year increments from date of birth to informed consent date.

#### **5.5.3. Study Day**

Study day will be computed as the date of assessment minus the Dosing date (plus one if the assessment date is on or after the dose date).

#### 5.5.4. Change and Percent Change from Baseline

Change from baseline will be computed as any post baseline follow-up value minus the baseline value.

Percent change from baseline will be computed as 100 times the (post-baseline value minus the baseline value) divided by the baseline value. If the baseline value or the post-baseline value is missing, change from baseline and percent change from baseline will be missing.

#### **5.5.5.** Prior and Concomitant Medications

Prior medications are those administered prior to F-DCFPyL administration date; concomitant medications are those administered from F-DCFPyL administration through last study visit. If the concomitant medication does not have a full date then the algorithm in Section 5.6.2 will be used to determine if it is a pre- or post-dose medication.

#### **5.5.6.** Treatment-Emergent Adverse Events

Treatment emergent AEs are defined for all subjects as AEs occurring from the day of, but after F-DCFPyL administration through the date prior to prostatectomy, lymphadenectomy, or change in planned procedure for subjects who underwent a procedure. For subjects who did not receive a procedure, TEAEs are collected up to 10 days after drug administration. For subjects in Cohort B who had a conventional imaging guided biopsy only, treatment emergent is defined as AEs occurring from the day of F-DCFPyL administration through 28 days post biopsy.

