5.2. Secondary Endpoints

- 1. Safety and tolerability (Cohorts A and B combined):
 - a. Treatment-emergent adverse events
 - b. Pre- and post-¹⁸F-DCFPyL PET/CT lab values, ECGs and vital signs
- 2. Sensitivity of ¹⁸F-DCFPyL PET/CT imaging to detect prostate cancer within sites of metastasis or local recurrence relative to histopathology (Cohorts B)
- 3. Comparison of detection rates (Cohorts A and B combined) for lesion counts overall and by location (i.e., bone, lymph nodes, soft tissue, prostate gland) between ¹⁸F-DCFPyL and conventional imaging
- 4. PPV and NPV of ¹⁸F-DCFPyL PET/CT imaging (Cohort A) to predict prostate cancer within the prostate gland and lymph nodes
- 5. PPV of ¹⁸F-DCFPyL PET/CT imaging to predict prostate cancer within sites of local recurrence and other metastatic lesions (cohort B)
- 6. Pharmacokinetic parameters [e.g., C_{max}, area under the curve (AUC), total clearance (CL), steady-state volume of distribution (V_{ss}) and mean residence time (MRT)] (subset of Cohorts A and B combined)

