¹ To be collected prior to dosing, if collected on day of dosing. If PSA and testosterone have not been tested within 30 days of study drug injection, a blood draw will be collected prior to dosing.

² If not obtained as standard of care ≤ 6 weeks (Cohort A) or ≤ 4 weeks (Cohort B) prior to Day 1. Na-¹⁸F-PET bone scans conducted at screening must be at least 10 hours prior to dosing (see Section 7.2).

³ Surgery or biopsy to occur at least 12 hours from time of ¹⁸F-DCFPyL dosing but not more than 28 days from dosing. In Cohort B, imaging used to guide biopsy (i.e., CT, MRI) will be submitted to a central core imaging lab.
 ⁴ See Section 10.6 for complete details. Analysis should occur immediately following last sample collected.

⁵ A safety phone call will also occur 7(\pm 3) days post-dosing [if surgery (Cohort A) or biopsy (Cohort B) has not yet occurred] and 21(\pm 7) days post biopsy (Cohort B). See Section 11.2.1.1 for complete details.

⁶ If a subject's planned procedure (RP or biopsy) for prostate cancer changes following ¹⁸F-DCFPyL imaging, the alternate or additional prostate cancer procedure and corresponding histopathology data will be recorded in the electronic case report form (eCRF).

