**Table 2: Schedule of Assessments** 

	Screening/ Baseline	 F-DCFPyL Dosing	 F-DCFPyL Imaging	Pre-Surgery/ Biopsy Follow-Up	
	Day -30 to Day 1	Day 1	1-2 Hours Post-Dosing	Within 28 Days Post- Dosing	
Adverse Events		2	X	X 	
Concomitant Medications	X	X		X	
Conventional Imaging (CT or MRI, bone scan)	X 				
Surgery or Image-Guided Biopsy				X 	
Subset of Cohort A or B at Johns Hopkins Universi	Subset of Cohort A or B at Johns Hopkins University only for PK Analysis				
Blood Collection		X  (9 collections)			
Urine Collection		X  (3 collections)			
Whole Body PET/CT			X  (3 scans)		

 To be collected prior to dosing, if collected on day of dosing. If PSA and testosterone have not been tested within 30 days of study drug injection, a blood draw will be collected prior to dosing.

- 3 Surgery or biopsy to occur at least 12 hours from time of F-DCFPyL dosing but not more than 28 days from dosing. In Cohort B, imaging used to guide biopsy (i.e., CT, MRI) will be submitted to a central core imaging lab.
- 4 Analysis should occur immediately following last sample collected.
- 5 A safety phone call will also occur  $7(\pm 3)$  days post dosing [if surgery, biopsy or a change in planned protocol procedure has not yet occurred] and  $21(\pm 7)$  days post biopsy for just the subjects who had a conventional image guided biopsy in Cohort B.
-  If a subject's planned procedure (RP or biopsy) for prostate cancer changes following F-DCFPyL imaging, the alternate or additional prostate cancer procedure and corresponding histopathology data will be recorded in the electronic case report form (eCRF).

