# 8.1. Adverse Event Preferred Term and System Organ Class Summary Tables

An overall summary of frequency and percentage of treatment-emergent adverse events (TEAEs), most frequent (>5%) overall TEAEs, serious TEAEs, severe TEAEs (grade  $\geq$  3), TEAEs by grade, and treatment-related TEAEs will be presented by cohort and overall using the safety set.

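### The pooled adverse-event tables count events after biopsy in Cohort B but leave out events after surgery in Cohort A

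*SAP*

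**What the plan says.** SAP 5.5.6 sets three windows for treatment-emergent adverse events (TEAEs):

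- Subjects who have surgery or a changed procedure are counted from after dosing "through the date prior to prostatectomy, lymphadenectomy, or change in planned procedure for subjects who underwent a procedure".
- The SAP gives a fixed limit where there is no procedure: "For subjects who did not receive a procedure, TEAEs are collected up to 10 days after drug administration".
- For Cohort B subjects whose only procedure was an image-guided biopsy, the window is the day of tracer "administration through 28 days post biopsy".

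The last window matches the visit plan. Footnote 5 to SAP Table 2 schedules a safety call 21 (±7) "days post biopsy for just the subjects who had a conventional image guided biopsy in Cohort B". Protocol 12.3.5 likewise goes past the procedure in Cohort B only. Footnote 3 to Protocol Table 3 places surgery or biopsy at least 12 hours after "dosing but not more than 28 days from dosing".

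The windows are then pooled. Protocol 5.2 gives the endpoint as "Safety and tolerability (Cohorts A and B combined". SAP 5.1 adds an overall column to the safety tables, and SAP 8.1 states that the TEAE summaries "will be presented by cohort and overall using the safety set". Table 14.3.1-2 selects terms that exceed 5% overall. The title of Table 14.3.1-7, on severity grade, names only the overall population, although the text of SAP 8.1.1 asks for cohorts as well.

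Neither document applies a common window to the pooled displays or splits Cohort B events at the biopsy.

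**The concern.** The safety objective concerns the tracer. It is given once, and SAP 5.5.10 models its decay with a 110-minute half-life. Both cohorts go on to an invasive procedure. Under SAP 5.5.6 the consequences of that procedure are treatment-emergent after a biopsy and not treatment-emergent after a prostatectomy.

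The pooled all-cause figure therefore measures neither tolerability of the tracer before any procedure nor tolerability of tracer plus procedure. It also changes with the share of subjects biopsied and with biopsy timing, even if the tracer behaves identically in both cohorts. The displays affected are the overall column, the list of frequent terms and the pooled severity table.

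**Working it through.** **Inputs from the documents.** About 262 subjects dosed in Cohort A and 115 in Cohort B (Protocol 6.2); procedure from 12 hours to 28 days after dosing; windows from SAP 5.5.6. The plan's own figures agree: 262 + 115 = 377, and the 28-day limit equals the latest time of the post-biopsy call, 21 + 7. Cohort B is 115/377 = 30.5% of subjects.

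**Step 1: longest windows after dosing.** Operated Cohort A: 28 − 1 = 27 days. Biopsied Cohort B: 28 + 28 = 56 days. No procedure: 10 days.

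**Step 2: share of observation time.** Assume for simplicity that every subject has the planned procedure on the same day t. Cohort A then has t − 1 days, Cohort B has t + 28, and Cohort B's share of pooled days is 115(t + 28) / [262(t − 1) + 115(t + 28)].

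| t | A days | B days | Post-biopsy part of B | B share of pooled days |
|---|---|---|---|---|
| 7 | 6 | 35 | 80% | 4025/5597 = 72% |
| 14 | 13 | 42 | 67% | 4830/8236 = 59% |
| 28 | 27 | 56 | 50% | 6440/13514 = 48% |

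With 30.5% of the subjects, Cohort B would supply roughly half to almost three quarters of the time at risk.

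**Step 3: effect on the pooled rate (illustration).** The documents give no TEAE or biopsy-complication rates, so these are assumed. Let a proportion *d* of each cohort have an event before the procedure and a proportion *q* of Cohort B have one after biopsy, independently. Then B = 1 − (1 − d)(1 − q), and pooled = (262d + 115B)/377. A common pre-procedure window would give *d*.

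| d | q | B | Pooled as planned | Common window |
|---|---|---|---|---|
| 10% | 5% | 14.5% | 11.4% | 10% |
| 10% | 20% | 28% | (26.2 + 32.2)/377 = 15.5% | 10% |
| 10% | 40% | 46% | 21.0% | 10% |
| 5% | 10% | 14.5% | 7.9% | 5% |
| 5% | 20% | 24% | (13.1 + 27.6)/377 = 10.8% | 5% |
| 5% | 30% | 33.5% | 13.7% | 5% |

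With d = 5% and q = 20%, a 50:50 cohort mix would give 14.5% and an 80:20 mix 8.8%.

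**Step 4: length alone.** Take d = 5%, no biopsy complications, a procedure on day 14 and a constant background hazard *h* per day. Then A = 1 − 0.95·exp(−13h) and B = 1 − 0.95·exp(−42h). At h = 0.002, A is 7.4%, B is 12.7% and the pooled rate is 9.0%. At h = 0.005 they are 11.0%, 23.0% and 14.6%. The common-window rate equals A in each case.

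**Step 5: the list above 5% overall.** 5% of 377 is 18.85, so a term needs 19 subjects. A term seen only after biopsy would need 19/115 = 16.5% of Cohort B.

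**Step 6: collection period.** Protocol 11.4 ends adverse-event collection at the visit before surgery or biopsy. Protocol 11.2.1.1 and 12.3.5 and SAP 5.5.6 continue past biopsy. These sections conflict, so it is unclear how completely post-biopsy events will be captured.

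**The case against.** The other side has several fair points.

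- **The displays are transparent.** SAP Section 8 summarises safety by cohort, so a reader sees A and B side by side. This stands, but a higher figure in B would not show whether tracer, biopsy or longer follow-up caused it.
- **Drug attribution has its own table.** Protocol 11.3 requires a related/unrelated judgement for each event, and Table 14.3.1-5 reports the related ones. A reader might infer that the pooled rate is offered as the tracer's own adverse-reaction rate. The documents do not support that: it is an all-cause rate. The mitigation is partial, because it rests on investigator judgement in an open-label study.
- **The asymmetry is prespecified.** The post-biopsy call is in the protocol, and Protocol 10.3 treats the Cohort A surgery as standard of care. Following subjects after biopsy is not an error. The problem lies in pooling the two windows.
- **No cohort comparison is planned.** A reader might infer that the windows spoil a comparison of tolerability between cohorts. No safety endpoint makes one, safety is descriptive, and the populations differ anyway.
- **The list of frequent terms is hard to distort.** A biopsy-only term needs 16.5% of Cohort B, so the effect there may be small. This stands.
- **The rates are assumed.** The only adverse-event experience in the documents is six events (Protocol 3.4), with 108 subjects dosed as of March 2016. That is at most 6/108 = 5.6% of subjects, if the counts refer to the same people. The direction in Step 3 is secure; the percentages are not evidence. Not every Cohort B subject will be biopsied, which reduces the effect.
- **A pre-procedure window is not of fixed length.** It runs from the dosing day alone to about 27 days. This stands, so the change removes the unequal treatment of procedure events but not every difference in follow-up time.

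**Conclusion.** The concern holds in a limited form. Applied as written, SAP 5.5.6 makes the overall column, the list of terms above 5% overall and the pooled severity table mix a window of at most about 27 days that excludes procedure events with one of up to about 56 days that includes them. The pooled all-cause rate contains biopsy complications but not surgical ones.

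The window lengths follow directly from the documents. The effect on the rate does not: under the assumed values in Step 3 the pooled rate exceeds the common-window rate by 1.4 to 11 percentage points, and the true figure depends on event rates that the documents do not give. The cohort columns and the drug-related table reduce the problem without removing it. No efficacy conclusion or formal test is affected.

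**What to change.** Amend the SAP before database lock:

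1. For the overall column, the list of terms above 5% overall and the pooled severity table, count TEAEs from after dosing to the day before the procedure in both cohorts. Keep the 10-day rule for subjects with no procedure. State in a footnote that window length still varies with procedure timing.
2. Add one table of Cohort B events from biopsy to 28 days after it. Where cohort columns stand beside the overall column, use the same window in all of them so that they add up.
3. Keep every event, including any post-biopsy event judged related, in the drug-related and serious-event tables and in the listings, and label the window used there.
4. Reconcile Protocol 11.4 with Protocol 11.2.1.1, Protocol 12.3.5 and SAP 5.5.6 on when adverse-event collection ends.

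Protocol 11.4 already records onset date and time, so the split needs no new data item. The cost is SAP wording, one extra table and an overall column that is less inclusive than now, which is why item 3 matters.

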### 5.5.7. Sensitivity, Specificity, PPV, and NPV

Sensitivity, specificity, PPV and NPV will be defined based on a F-DCFPyL image result (positive or negative) and a histopathology result (positive or negative).

Table 3: Classification of F-DCFPyL Imaging Result and Histopathology Result

	Histopatho		
 F-DCFPyL Image Positive* Negative			
Positive	TP	FP	I(p)
Negative	Negative FN		I(n)
	R(p)	R(n)	N

TP=true positive; FP=false positive; FN=false negative; TN=true negative.

The following statistics will be computed:

- Sensitivity = TP/R(p),
- Specificity = TN/R(n),
- Positive predictive value (PPV) = TP/I(p),
- Negative predictive value (NPV) = TN/I(n).

R(p) and R(n) denote the number of subjects with positive and negative histopathology results, respectively.

I(p) and I(n) denote the number of subjects with positive and negative F-DCFPyL images, respectively.

N indicates the number of subjects

\*positive histology should be for prostate cancer only

### 5.5.7.1. Primary Endpoints and Pelvic Lymph Nodes

The primary endpoints of sensitivity and specificity are defined from lymph node imaging results and corresponding pelvic lymph node histology. For an imaging result to be deemed positive for this endpoint, the tissue must have first been removed from that corresponding area. This ensures that an imaging result has the ability to align with the results achieved from pathology. This will be applied to Cohort A subjects only.

PPV and NPV will also be calculated as secondary endpoints from the pelvic lymph nodes. The same definitions used below will apply.

Criteria for Positive PyL Imaging Result	Criteria for Lymph Node Dissection and Positive Histology
If Right or Left Pelvic Lymph Nodes Minimum Template = Positive and  • Tissue was removed from left template and total left nodes removed ≥1 and Template Left Pelvic LN Lesion Count	≥1 positive lymph node on right template if Template Right Pelvic LN Lesion Count from imaging is ≥0 or ≥1 positive lymph nodes on left template if Template Left Pelvic LN Lesion Count from
≥1 or  • Tissue was removed from right template and total right nodes removed ≥1 and Template Right Pelvic LN Lesion Count ≥1  or  Tissue was removed from Pre-sacral nodes and total pre-sacral nodes removed ≥1 and Pre-Sacral Pelvic LN Lesion Count ≥ 1	imaging is ≥0 or ≥1 positive lymph nodes on pre-sacral nodes if Pre-Sacral Pelvic LN Lesion Count from imaging is ≥0 or ≥1positive lymph nodes on other pelvic lymph nodes if Other Pelvic Lymph Node Count from imaging is ≥0
or Tissue was removed from Other lymph nodes and Total nodes removed >=1 and Other Pelvic LN Lesion Count ≥ 1 or	

If tissue was removed from right template and total right nodes removed ≥1 and resection included tissue along the external iliac artery and Right pelvic lymph node external iliac artery= positive or

If tissue was removed from left template and total left nodes removed ≥1 and resection included tissue along the external iliac artery and left pelvic lymph node external iliac artery= positive or

If tissue was removed from right template and total right nodes removed ≥1 and resection included tissue along the common iliac vein and Right pelvic lymph node common iliac vein= positive or

If tissue was removed from left template and total left nodes removed ≥1 and resection included tissue along the common iliac vein and left pelvic lymph node common iliac vein=positive or

If tissue was removed from right template and total right nodes removed ≥1 and resection included tissue along the common iliac artery and Right pelvic lymph node common iliac artery= positive or

If tissue was removed from left template and total left nodes removed ≥1 and resection included tissue along the common iliac artery and left pelvic lymph node common iliac artery= positive

If Template Right Pelvic LN Lesion Count from imaging is  $\geq 0$  and Total number of positive lymph nodes from Right Template  $\geq 1$  or

If Template Left Pelvic LN Lesion Count from imaging is  $\geq 0$  and Total number of positive lymph nodes from Left Template  $\geq 1$ 

If any of the above criteria are met for imaging then PyL Imaging Result=Positive. If Cohort =A and lymphadenectomy was performed, and lesion counts from imaging results are available for at least one location (right, left, pre-sacral or other) but the above criteria are not met for imaging, then PyL Imaging Results = Negative.

If the above criteria for histology are met then Histology is positive. If all available positive lymph nodes=0 where the corresponding lesion count from imaging≥0 then Histology is negative.

If the lesion counts from all 4 locations (right, left, pre-sacral, and other lymph nodes) are not evaluable on imaging or tissue is not removed from all 4 locations then this endpoint will be missing.

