10.3. Prostatectomy and Lymphadenectomy

Within 28 days post-study drug injection, all subjects in Cohort A will undergo standard of care RP with PLND as detailed in the Surgical Manual. Extent of PLND will be captured in the eCRF.

Surgical staff will label all specimens removed during surgery to correlate with the specific anatomic location of removal, in accordance with the Surgical Manual.

Should a subject receive alternate or additional procedure(s) for prostate cancer after dosing, the procedure and corresponding histopathology data will be recorded in the eCRF.

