12.3. Endpoints and Derivations

12.3.1. Sensitivity, Specificity, PPV, and NPV

Table 7 will be used to classify the combined pelvic lymph node packets (left or right) from Cohort A and biopsy from Cohort B according to its ¹⁸F-DCFPyL image result (positive or negative) generated from central imaging review and its histopathology result (positive or negative for prostate cancer) generated by the sites' pathology review. Nodes identified on ¹⁸F-DCFPyL PET/CT images in areas that were not removed in surgery for Cohort A will not be tabulated due to absence of histopathology.

Table 7: Classification of ¹⁸F-DCFPyL Imaging Result and Histopathology Result for Cohorts A and B Separately

	Histopatho	ology Result	
¹⁸ F-DCFPyL Image	Positive*	Negative	
Positive	ТР	FP	I(p)
Negative	FN	TN	I(n)
	R(p)	R(n)	Nı

TP=true positive; FP=false positive; FN=false negative; TN=true negative.

R(p) and R(n) denote the subjects with a positive or negative lobe or biopsy, respectively, based on histopathology. I(p) and I(n) denote the subjects with a positive and negative lesion, respectively, based on the ¹⁸F-DCFPyL image. N_1 indicates the number of subjects with evaluable pelvic lymph node packets from Cohort A or the number of subjects with evaluable biopsies from Cohort B.

*Positive histopathology should be for prostate cancer only.

The following statistics will be computed:

- Sensitivity = TP/R(p),
- Specificity = TN/R(n),
- Positive predictive value (PPV) = TP/I(p),
- Negative predictive value (NPV) = TN/I(n).

For Cohort A, a true positive or true negative must be determined from imaging and histopathology aligning on outcome overall.

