#### 5.5.8. Lesions Per Subject

The number of lesions detected on imaging categorized as bone, lymph nodes, soft tissue, and the prostate gland will be determined by each of the central imaging core lab independent readers. The sum of lesions per subject per tissue type and overall will be computed for each subject based on each reader's lesion count. This will be calculated from the F-DCFPyL PET/CT scan results as well as the conventional imaging results.

Bone	Soft Tissue	Lymph nodes	Prostate Gland
BN Skull	ST Brain	LN Cervical	ST Prostate Gland Left
BN Thorax	ST Neck	LN Supraclavicular	ST Prostate Gland Right
BN Spine	ST Lungs	LN Axillary	
BN Pelvis	ST Esophageal	LN Mediastinal	
BN Extremities	ST Liver	LN Hilar	
	ST Gall Bladder	LN Mesenteric	
	ST Spleen	LN Elbow	
	ST Pancreas	LN Popliteal	
	ST Adrenal	LN Peri-aortic/para-aortic	
	ST Kidney	LN Other, Non-Pelvic	
	ST Bladder	PLN Template Right	
	ST Prostate Bed	PLN Template Left	
	ST Seminal Vesicle	PLN Pre-Sacral	
	ST Skin	PLN Other, Pelvic	
	ST Muscle		
	ST Other		

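### The Other-node row of the co-primary PET-positive rule lacks a site match and a region-specific node count, so a PET lesion at an unresected Other site can be scored as a false or true positive

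*SAP*

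**What the plan says.** SAP 5.5.7.1 opens with a general condition for a positive PET call in Cohort A: "the tissue must have first been removed from that corresponding area". Protocol 12.3.1 agrees: nodes seen on PET "in areas that were not removed in surgery for Cohort A will not be tabulated due to absence of histopathology".

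The rows that apply this condition differ in strictness:

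- **Left and right template rows:** tissue from that side, at least one node from that side, and a PET lesion count of at least 1 on that side.
- **Pre-sacral row:** "Tissue was removed from Pre-sacral nodes and total pre-sacral nodes removed ≥1 and Pre-Sacral Pelvic LN Lesion Count ≥ 1".
- **Iliac rows:** matched by side and named vessel, for example "resection included tissue along the external iliac artery and Right pelvic lymph node external iliac artery= positive".
- **Other row:** "Tissue was removed from Other lymph nodes and Total nodes removed >=1 and Other Pelvic LN Lesion Count" of at least 1.

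On imaging, SAP 5.5.8 holds these lesions in one unsided category, "PLN Other, Pelvic". Meeting any one row makes the subject PET-positive. SAP 7.6.1 analyses one overall outcome per subject.

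**The concern.** Other is whatever remains after the named regions, both on PET and at surgery, so two different sites can carry the same label. The row then treats a PET lesion at one unlisted site as resected because tissue was taken from another. Its node condition is also looser than its neighbours': read literally, a count with no region word is met by template nodes, even if the Other specimen held no node.

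Such a call has no pathology at its own site, yet it enters both co-primary endpoints. In a subject whose evaluated nodes are all negative it gives a false positive and lowers specificity. In a subject with a positive node elsewhere that PET missed, it gives a true positive and raises sensitivity. Both outcomes are contrary to the SAP's opening condition and to Protocol 12.3.1.

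**Working it through.** **1. When the row gives the wrong answer.** All of these must hold together:

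- some Other tissue was removed;
- the node count is satisfied;
- the reader records an Other pelvic lesion;
- that lesion lies at a site the surgeon did not resect;
- no other row already makes the subject positive.

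**2. The plan's own sample size.** SAP 4.3 uses n = {[z(α/2)√(P0(1−P0)) + z(β)√(P1(1−P1))] / (P1−P0)}², with two-sided 5%, 80% power and 20% prevalence.

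- Sensitivity, 0.40 against 0.60: 47.09 node-positives; 47.09/0.20 = 235.5, so 236.
- Specificity, 0.80 against 0.878: 184.5 node-negatives; 184.5/0.80 = 230.6, so 231.
- The larger is 236, and 236/0.90 = 262.2, about 262. The stated 236 and 262 reproduce.

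Expected counts at 236 evaluable are 236 × 0.20 = 47.2 positives and 236 × 0.80 = 188.8 negatives. I use 47 and 189.

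**3. Pass marks per reader.** SAP 7.6.1 needs the lower 95% limit, by the normal approximation, to exceed 0.80 and 0.40: p̂ − 1.96√(p̂(1−p̂)/n).

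- Specificity, n = 189: 160 gives a limit of 0.795 (fail); 161 gives 0.801 (pass).
- Sensitivity, n = 47: 25 gives 0.389 (fail); 26 gives 0.411 (pass).

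**4. Effect of k affected subjects.** The documents do not say how often this occurs, so k is an assumed range. One subject moves specificity by at most 1/189 = 0.53 percentage points and sensitivity by at most 1/47 = 2.1 points. Fixing k subjects at the wrong or unearned result and leaving the rest binomial gives:

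| k | Specificity: P(Bin(189−k, 0.878) ≥ 161) | Sensitivity: P(Bin(47−k, 0.40) ≥ 26−k) |
|---|---|---|
| 0 | 0.885 | 0.024 |
| 1 | 0.846 | 0.034 |
| 2 | 0.798 | 0.048 |
| 3 | 0.741 | 0.067 |
| 4 | 0.676 | not computed |

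The specificity column is the chance of passing at the planned alternative. The sensitivity column is the chance of passing when true sensitivity equals the null.

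**The case against.** The strongest reply is that the opening condition of SAP 5.5.7.1 governs every row, and Protocol 12.3.1 supports it. On that view the Other row fails to spell out a rule but does not override it. This shows the intent. It does not tell a programmer how to apply it, because the row is the operative derivation and the rows beside it do carry the match.

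Five stronger readings are tempting, and the documents do not support them:

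- **That PET lesions at unresected Other sites are scored positive as a rule.** The row still requires Other tissue to have been removed. A subject with no Other resection does not meet it.
- **That the node count is certainly the overall total.** That is the literal reading, but the phrase follows directly on Other tissue and may mean Other nodes only. Likewise, surgical Other nodes need not extend beyond the pelvis: the section title and the histology column both say pelvic. These are ambiguities. The missing site match remains on either reading.
- **That the whole sensitivity effect belongs to this row.** If the positive nodes lie in a template or pre-sacral region, the credit arises because PET and histology are pooled over the subject, and region-level scoring would remove it. Only a histology-positive Other specimen at a different site would survive that change.
- **That an unresected iliac lesion is always coded negative while an Other lesion is not.** SAP 5.5.8 does not show which count category holds iliac lesions. The contrast in the wording of the rows stands; a contrast in outcome is not shown.
- **That false trial success rises to the tabulated rates.** The figures are per reader and per endpoint. Success needs specificity first and then sensitivity from the same two readers, and the same gap makes specificity harder to pass.

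**Conclusion.** The point holds as a defect in a stated co-primary derivation. Applied as written, the Other row can make a subject PET-positive on a lesion with no pathology at its site. It has no side or sub-site match, and its node count names no region.

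The frequency and net direction cannot be fixed from the documents: specificity is pushed down and sensitivity up. The sizes rest on 189 and 47 evaluable subjects, the normal-approximation limit and an assumed number of affected subjects. On that basis a few cases matter per reader. Two affected node-negatives take the chance of passing specificity below 0.80. Two affected node-positives double the sensitivity pass rate at the null (0.024 to 0.048), though part of that effect belongs to pooled scoring. The row should be corrected before database lock.

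**What to change.** 1. Change the node condition in the Other row to total Other pelvic nodes removed of at least 1.
2. Count an Other PET lesion as positive only if its recorded side and sub-site match a resected Other pelvic specimen. Do the matching before database lock and blind to histology, from the reader's recorded location and the specimen labels that Protocol 10.3 already requires ("Surgical staff will label all specimens removed during surgery to correlate with the specific anatomic location of removal"). Treat an unmatched lesion like any PET lesion in an unresected area.
3. Where no PET sub-site is recorded, keep the row and add a prespecified sensitivity analysis of both co-primary endpoints that drops it.

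The cost is revised SAP wording, some documented matching judgements and one extra analysis. It cannot be assumed that the PET sub-site already exists: the only PET field shown is the single count in SAP 5.5.8, and the Imaging Manual, Imaging Review Charter and Surgical Manual were not among the documents. Step 3 covers that gap.
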